**Table 7 Study Flow Chart: Part B** 

	Screening	Admissi on			IMP I	Oosing P	eriod			Discharge	Post Study Follow-up		
Study Day	D-28 to D-3	D-2	D-1	D1	D2	D3	D4	D5	D6	D7 (last dosing +2 days)	D19-D23 (last dosing + 14-18 days)		
General Assessments													
Informed consent	X												
Medical and surgical history	X												
Demographic data	X												
Hepatitis/HIV serology	X												
PCR test COVID- 19		X											
Inclusion/Exclusion criteria 	X	X		X	X	X	X	X					
Weight and height	X									X (Weight only)			
Vein assessment	X												
Urine drugs of abuse and alcohol/cotinine screen	X	X											
Randomisation				X									
IMP administration				X	X	X	X	X					

# Clinical Study Protocol

Confidential

Final V3.0/ Date 07 December 2020

Page 71 of 109

	Screening	Admissio n				Dosing Pe	Clinical U eriod	IIIt		Discharge	Post Study Follow-up
Study Day	D-28 to D-3	D-2	D-1	D1	D2	D3	D4	D5	D6	D7 (last dosing +2 days)	D19-D23 (last dosing + 14-18 days)
Safety Assessments					•			,			
Physical examination 	X (Full)	X (Brief)					X (Brief)			X (Brief)	X (Brief)
Laboratory safety tests (biochemistry, haematology, coagulation, urinalysis and urine microscopy) 	X	X			X		X	X		X	X
Troponin I 		X						X			
FSH (Post- menopausal female subjects only)	X										
Holter monitoring (for extraction of ECGs) 			X					X			
12-lead ECG 	X	X		X			X	X		X	
Vital signs 	X	X		X			X	X		X	X
Adverse events	X	X	X	X	X	X	X	X	X	X	X
Serious adverse events	X	X	X	X	X	X	X	X	X	X	X
Prior and concomitant medication	X	X	X	X	X	X	X	X	X	X	X

### Clinical Study Protocol

Confidential

Final V3.0/ Date 07 December 2020

Page 72 of 109

			Resident in the Clinical Unit												
	Screening	Admission			IMP D	osing Po	eriod			Discharge	Post Study Follow-up				
Study Day	D-28 to D-3	D-2	D-1	D1	D2	D3	D4	D5	D6	D7 (last dosing +2 days)	D19-D23 (last dosing + 14-18 days)				
Pharmacokinetic Assessments															
Plasma samples for DNDI-0690 and metabolite 				X	X	X	X	X	X	X					
DBS samples for DNDI-06909				X				X	X	X					
Urine samples for DNDI-0690 				X				X							
Other assessments		_													
Urine samples for exploratory biomarkers 				X	X		X	X							

#### **Study Flow Chart Footnotes:**

- 1. Full inclusion/exclusion criteria will be checked at Screening. Eligibility will be re-confirmed on Day -2 and prior to each dose administration.
- 2. Physical examination: Full physical examination will be performed at Screening. A brief physical examination will be performed on Day -2, Day 4, Day 7 and Post Study follow-up.
- 3. Laboratory safety tests will be performed at Screening, Day -2, pre-dose on Day 2/Day 4/Day 5, Day 7 and Post Study follow-up. Glomerular Filtration Rate (GFR) will be estimated at Screening for eligibility purposes and at each time point, using the CKD-EPI equation. GFR based on Cys C results (GFRcc) will also be assessed.
- 4. Troponin I sample will be taken at Day -2 and Day 5 (Pre-dose).
- 5. Holter monitoring will begin 60 minutes prior to the theoretical Day 1 dosing time on Day -1 and begin approximately 60 minutes prior to dosing on Day 5. Holter recording will end any time after Day 1 dosing and end any time after Day 6 (24 h) post-last dose PK sample collection. One set of triplicate ECG extractions to be taken at pre-dose (for baseline; T-30min to T-15 min) and at 0.5, 1, 2, 3, 3.5, 4, 6, 9, 12 and 24 h post-dose, time-matched on Day 5 timepoints for the Day-1 timepoints. Extractions are always done within the 10 minutes prior to PK sampling, except at pre-dose.
- 6. 12-lead ECGs will be taken at Screening, Day -2, Day 1/Day4/Day 5 (pre-each dose and 4 h post-dose) and Day 7. Day 1, pre-dose ECG will be taken in triplicate (for baseline), all post-dose time points will be single ECG. An ECG can be repeated for any reason (technical in particular).
- 7. Vital signs (supine blood pressure, heart rate and Tympanic temperature) will be measured at Screening, Day -2, pre-dose on Day 1/Day 4/Day 5, Day 7 and Post Study follow-up.
- 8. Plasma samples for DNDI-0690 and metabolite will be taken (4 mL K2EDTA tube) on Day 1 (pre-dose and 0.5, 1, 2, 3, 3.5, 4, 6, 9, 12 h post-dose), pre-dose on Day 2/Day 3/Day 4 and Day 5 (pre-dose and 0.5, 1, 2, 3, 3.5, 4, 6, 9, 12 h post-dose), Day 6 (24h post-last dose) and Day 7 (48h post-last dose).
- 9. Dried blood spot (DBS) samples for DNDI-0690 will be taken (2 mL K2EDTA vacuum tube) on Day 1 (pre-dose, 0.5, 1 and 2 h post-dose) and Day 5 (pre-dose and 0.5, 1, 2, 3, 3.5, 4, 6, 9, 12 h post-dose), Day 6 (24 h post-last dose) and Day 7 (48 h post-last dose).
- 10. Urine samples for DNDI-0690 will be collected on Day 1 (pre-dose and 0-24h post-dose) and on Day 5 (0-24h post-dose).
- 11. Urine samples for exploratory biomarkers (Cys C, Kidney Injury Molecule-1 (KIM-1) and Neutrophil Gelatinase-Associated Lipocalin (NGAL)) will be collected at pre-dose on Day 1/Day 2/Day 4/Day 5 (from spot collection).

Clinical Study Protocol

Confidential

Final V3.0/ Date 07 December 2020

Page 73 of 109

Table 8 Study Flow Chart: Part C

			Resident in the Clinical Unit													
	Screening	Admission	Iohexol Baseline						Dosing						Discharge	Post Study Follow-up
Study Day	D-28 to D-3	D-2	D-1	D1	D2	D3	D4	D5	D6	D7	D8	D9	D10	D11	D12 (last dosing +2 days)	D24-D28 last dosing + 14- 18 days)
General Assessments									•	•			,	,		
Informed consent	X															
Medical and surgical history	X															
Demographic data	X															
Hepatitis/HIV serology	X															
PCR test COVID-19		X														
Inclusion/Exclusion criteria 	X	X		X	X	X	X	X	X	X	X	X	X			
Weight and height	X														X (Weight only)	
Vein assessment	X	X														
Urine drugs of abuse and alcohol/cotinine screen	X	X														
Randomisation				X												
Iohexol administration 			X										X			X (optional)
IMP administration				X	X	X	X	X	X	X	X	X	X			
Safety Assessments																
Physical examination 	X (Full)	X (Brief)	X (Brief)				X (Brief)			X (Brief)					X (Brief)	X (Brief)
Laboratory safety tests (biochemistry, haematology, coagulation, urinalysis and urine microscopy) 	X	X			X		X			X			X		X	X
Troponin I 		X		X									X			
FSH (post-menopausal female subjects only)	X															

# Clinical Study Protocol

Confidential

Final V3.0/ Date 07 December 2020

Page 74 of 109

							Reside	nt in the	e Clinic	al Unit						
	Screening	Admission	Iohexol Baseline					IMP	Dosing	Period					Discharge	Post Study Follow-up
Study Day	D-28 to D-3	D-2	D-1	D1	D2	D3	D4	D5	D6	D7	D8	D9	D10	D11	D12 (last dosing +2 days)	D24-D28 last dosing + 14- 18 days)
12-lead ECG 	X	X	X	X			X			X			X		X	
Vital signs 	X	X	X	X			X			X			X		X	X
Adverse events	X	X	X	X	X	X	X	X	X	X	X	X	X	X	X	X
Serious adverse events	X	X	X	X	X	X	X	X	X	X	X	X	X	X	X	X
Prior and concomitant medication	X	X	X	X	X	X	X	X	X	X	X	X	X	X	X	X
Pharmacokinetic Assessments																
Plasma samples for DNDI-0690 and metabolite 				X	X		X			X			X	X	X	
Plasma samples for iohexol 			X										X			X (optional)
Urine samples for iohexol 			X										X			X (optional)
Urine samples for exploratory biomarkers 				X	X		X			X			X			•

#### **Study Flow Chart Footnotes:**

- 1. Full inclusion/exclusion criteria will be checked at Screening. Eligibility will be re-confirmed on Day -2 and prior to each dose administration.
- 2. Iohexol administration: All subjects will receive 5 mL of iohexol solution (300 mg/mL iodine) intravenously on Day -1, Day 10, and optionally on Day 24-28 (Post Study follow-up) that will be flushed with 10 mL of normal saline solution. On Day -1, iohexol solution will be administered at the same time as expected dosing of the study drug or placebo on Day 10. On Day 10, iohexol solution will be administered immediately after dosing of study drug or placebo.
- 3. Physical examination: Full physical examination will be performed at Screening. A brief physical examination will be performed on Day -2, Day -1, Day 4, Day 7, Day 12 and Post Study follow-up.
- 4. Laboratory safety tests will be performed at Screening, Day -2, pre-morning dose on Day 2/ Day 4/Day 7/Day 10, Day 12 and Post Study follow-up. Glomerular Filtration Rate (GFR) will be estimated at Screening for eligibility purposes and at each time point, using the CKD-EPI equation. GFR based on Cys C results (GFRcc) will also be assessed.
- 5. Troponin I samples will be taken on Day -2, Day 1 (pre-morning dose) and Day 10 (Pre-last dose).
- 6. 12-lead ECGs will be taken at Screening, Day -2, Day -1 (pre-iohexol dose), Day 1/Day 4/Day 7/Day 10 (pre-morning dose and 4 h post-morning dose) and Day 12. Day 1, pre-morning dose ECG will be taken in triplicate (for baseline), all post-dose time points will be single ECG. An ECG can be repeated for any reason (technical in particular).
- 7. Vital signs (supine blood pressure, heart rate and Tympanic temperature) will be measured at Screening, Day -2, Day -1 (pre-iohexol dose), pre-morning dose on Day 1/Day 4/Day 7/Day 10, Day 12 and Post Study follow-up.
- 8. Plasma samples for DNDI-0690 and metabolite will be taken (4 mL K2EDTA tube) at pre-morning dose on Day 1/Day 2/Day 4/Day 7 and Day 10 (pre-last dose and 0.5, 1, 2, 3, 4, 6, and 9 h post-last dose), Day 11 (24h post-last dose) and Day 12 (48h post-last dose).

Clinical Study Protocol

Final V3.0/ Date 07 December 2020

Confidential

Page 75 of 109

- 9. Plasma samples for iohexol will be taken (5 mL lithium heparinized tube) at pre-iohexol dose, 1, 2, 3, 4 and 5 h post-iohexol dose on Day -1 and Day 10 and optional at Follow-up visit. Follow-up samples are needed only when results from previous timepoints of GFR calculation or urine microscopy showed abnormal results.
- 10. Urine samples for iohexol: Pre-iohexol dose, [0-1], [1-2], [2-3], [3-4] and [4-5] h post-iohexol dose on Day -1, Day 10 and optional at Follow-up visit. Follow-up samples are needed only when results from previous timepoints of GFR calculation or urine microscopy showed abnormal results.
- 11. Urine samples for exploratory biomarkers (Cys C, Kidney Injury Molecule-1 (KIM-1), neutrophil gelatinase-associated lipocalin (NGAL)) will be collected at pre-morning dose on Day 1/Day 2/Day 4/Day 7/Day 10 (from morning spot collection).

Final V3.0/ Date 07 December 2020

Confidential

Page 76 of 109

#### 10.7.2 Demographic and Background Assessments

The following demographic and background assessments will be performed during the study at the time-points specified in Table 6, Table 7 and Table 8.

#### 10.7.2.1 Demographics

**DNDi** 

RD 777/34920

DNDi- 0690- 02

Demographic data: age, date of birth (only year of birth is recorded in the CRF), gender, race, height, weight and BMI.

Height in metres (to the nearest cm) and weight in kg (to the nearest 0.1 kg) in indoor clothing and without shoes will be measured. BMI = body weight (kg) / [height (m)] will be calculated.

#### 10.7.2.2 Medical and Surgical History

Relevant medical and surgical history will be recorded in the CRF.

#### 10.7.2.3 Virology Tests

Virology tests: HBsAg, HCV Ab and HIV test (antibodies to HIV-1 and HIV-2).

Virology tests will be analysed from the same serum sample for biochemistry analyses at Screening by Simbec-Orion Laboratory Services, or at an appropriate referral laboratory, using an appropriate analyser/method(s) of analyses.

#### 10.7.2.4 PCR Test COVID-19

The POC Menarini vita PCR analyser will be used to determine the COVID-19 status using nasopharyngeal/oropharyngeal swab.

#### 10.7.2.5 Drugs of Abuse (including Alcohol and Cotinine)

Urine DOA screen (including alcohol and cotinine):

- Alcohol
- Cotinine
- Amphetamines
- Barbiturates
- Benzodiazepines
- Cocaine
- Marijuana/Cannabis
- Methadone
- Methamphetamine (reported under Amphetamine test)
- Ecstasy (reported under Amphetamine test)
- Morphine/Opiates
- Phencyclidine
- Tricyclic Antidepressants

A mid-stream urine sample will be collected into a universal collection/storage container. At protocol-defined time-points when both urinalysis and DOA / alcohol and cotinine Screening

DNDi RD 777/34920 DNDi- 0690- 02

Final V3.0/ Date 07 December 2020

Confidential

Page 77 of 109

are required, all urine analyses will be performed from a single approximately 30 mL urine sample.

Urine samples for DOA (including alcohol and cotinine) will be analysed by Simbec-Orion Laboratory Services, or at an appropriate referral laboratory, using an appropriate analyser/manual kit(s)/method(s) of analyses.

Assessments of urine sample quality (*i.e.* urine sample verification/adulteration) will be performed by measuring urine creatinine for urine DOA.

#### 10.7.2.6 Pregnancy Test, Menstrual and Obstetric History

Pregnancy test is not needed. Only WONCBP females will be included in this study.

Date and method of permanently sterilization will be recorded in the eCRF.

#### 10.7.2.7 FSH

Serum FSH will be analysed from the same serum sample for biochemistry analyses at Screening for postmenopausal females only. **Serum** FSH analysis will be performed by Simbec-Orion Laboratory Services, or at an appropriate referral laboratory, using an appropriate analyser/method(s) of analysis.

#### 10.7.2.8 Compliance with Inclusion/Exclusion Criteria

An Investigator will assess all participants against the study inclusion and exclusion criteria at Screening. Compliance will be re-confirmed on Day -2.

## 10.7.3 Efficacy Assessments

Not applicable.

#### **10.7.4 Safety Assessments**

Safety assessments will be performed at the time-points specified in Table 6, Table 7 and Table 8.

#### **10.7.4.1 Definitions**

#### **Adverse Events:**

An AE is any untoward medical occurrence in a patient or clinical trial subject administered an IMP, which does not necessarily have a causal relationship with this treatment.

It can therefore be any unfavourable and unintended sign (*i.e.* an abnormal laboratory finding), symptom, or disease temporally associated with the use of a medicinal product, whether or not considered related to the medicinal product.

Definition of an AE includes worsening (in severity and frequency) of pre-existing conditions ("Medical history") before first IMP administration and abnormalities of procedures (*i.e.* 12-lead ECG results) or abnormal laboratory results which are assessed as "clinically significant".

Final V3.0/ Date 07 December 2020

Confidential

Page 78 of 109

DNDi RD 777/34920 DNDi- 0690- 02

#### Clinically Significant Laboratory Procedures/Abnormalities:

For every laboratory assessment, the Investigator will evaluate if the laboratory test result is normal or abnormal. If abnormal (after repeat test as required), the Investigator will assess if this finding is clinically significant or not. If a laboratory parameter is abnormal and clinically significant, it should be reported as an AE.

An abnormal laboratory/procedure result must be compared with the previous value taking into account normal values in the studied population/country.

A TEAE is a new event after the administration of the first dose of the study drug or a worsening in the condition. In the case of abnormal laboratory/procedure tests results, it is an increase in severity (clinical intensity) of the abnormality which is judged clinically significant by the Investigator.

Any abnormalities will be assessed as "clinically significant" (and therefore have to be reported as an AE) if they meet at least one of the following conditions:

- The abnormality suggests a disease and/or organ toxicity AND this abnormality was
  not present at the Screening visit or is assessed as having evolved since the
  Screening visit,
- The abnormality requires medical intervention or concomitant therapy,
- Furthermore, laboratory abnormalities associated with clinical signs and symptoms will also be considered clinically significant.

When reporting an abnormal laboratory result as an AE, a clinical diagnosis should be recorded rather than the abnormal value itself, if available. However, in these cases, the AE should be recorded as the syndromic clinical diagnosis (*i.e.* acute pancreatitis instead of each finding separately: high levels of amylase, high levels of lipase, abdominal pain and vomiting; "hypokalaemia" rather than "decreased potassium levels").

#### **Adverse Drug Reaction:**

An adverse drug reaction (ADR) is any AE where a causal relationship with the IMP is at least a reasonable possibility (possibly related, probably related or definitely related). This means that there are facts (evidence) or arguments to suggest a causal relationship between the event and the IMP (see definition of causality below).

#### **Serious Adverse Events:**

An SAE is defined as any untoward medical occurrence that at any dose:

- results in death
- is life-threatening (at the time of the event): in this context refers to an AE in which the patient was at risk of death at the time of the AE; it does not refer to an AE that hypothetically might have caused death if more severe;
- requires hospitalization or prolongation of existing hospitalization: *i.e.* the AE requires at least an overnight admission or prolongs a hospitalisation beyond the expected length of stay;

DNDi RD 777/34920 DNDi- 0690- 02

Final V3.0/ Date 07 December 2020

Confidential

Page 79 of 109

- results in persistent or significant disability or incapacity: *i.e.*, the AE resulted in a substantial disruption of the subject's ability to conduct normal activities;
- consists of a congenital anomaly or birth defect: *i.e.*, an AE outcome in a child or foetus of a subject exposed to the IMP before conception or during pregnancy;
- an important medical event as recognised by the PI: *i.e.*, AE is medically significant: medical and scientific judgment should be exercised in deciding whether other situations should be considered serious events/reactions, such as important medical event that may not be immediately life-threatening or results in death or hospitalization but may jeopardize the subject or may require intervention to prevent one of the other outcomes listed in the above definition should also usually be considered as serious. In addition, any suspected transmission via a medicinal product of an infectious agent is also considered a SAE/reaction.

#### **Unexpected Adverse Reaction:**

An unexpected adverse reaction is an adverse reaction, whose nature, severity or outcome is not consistent with the applicable product safety reference information on the IMP *i.e.* the IB.

#### **Suspected Unexpected Serious Adverse Reactions (SUSARs):**

SUSARs are SAEs which are believed to be related to an IMP and are both unexpected (*i.e.* the nature or severity is not expected from the information provided in the IB) and serious. SUSARs are subject to expedited reporting to the MHRA, EMA and EC.

# **Reference Documents for Expectedness Assessment:**

The reference document for expectedness assessment of SAE related to study product for the present study is the IB currently in force at the time of SAE occurrence.

#### 10.7.4.2 Adverse Events

## 10.7.4.2.1 Recording Adverse Events

AEs will be recorded from the time of providing written informed consent until discharge from the study at the follow-up visit.

Any untoward medical event which occurs after the completion of the clinical trial and is reported by the subject to Simbec-Orion will be classified as a "post-study event". All serious post study events assessed as related to the IMP will be reported to the pharmacovigilance of the Sponsor.

During each study visit the subject will be questioned directly regarding the occurrence of any adverse medical event according to the schedule in the source. All AEs, whether ascribed to study procedures or not, will be documented immediately in the source. This will include the date and time of onset, a description of the AE, severity, duration, actions taken, outcome and an Investigator's current opinion on the relationship between the study drug and the event. A diagnosis and final opinion on the relationship between the study drug and the event will be provided at the end of the study by the Investigator.

DNDi RD 777/34920 DNDi- 0690- 02

Final V3.0/ Date 07 December 2020

Confidential

Page 80 of 109

Any subject who withdraws from the study due to an AE will be followed up until the outcome is determined and written reports provided by the Investigator.

#### 10.7.4.2.2 Analysis of Events by the Investigator

Each AE is to be classified by the Investigator (in this order):

- For severity
- For causality
- As serious or non-serious

# **Grading of Adverse Event Severity**

The Investigator will evaluate each event with regard to its severity. The severity of the AEs will be determined in the following manner:

- Mild: An AE that is easily tolerated by the subject, causes minimal discomfort, and does not interfere with everyday activities
- Moderate: An AE that is sufficiently discomforting to interfere with normal everyday activities; intervention may be needed
- Severe: An AE that prevents normal everyday activities; treatment or other intervention usually needed
- Life-Threatening: The subject is at significant risk of life; it does not refer to an event which hypothetically might have caused death if it were more severe (life threatening consequences, urgent intervention required).
- Death: Death related to an event.

When the severity of an AE changes over time, only one AE and the maximum severity will be recorded in the eCRF for each separate event. If the AE resolves but then recurs, each will be recorded as a separate AE, with the appropriate start and stop times.

To ensure no confusion or misunderstanding of the difference between the terms "serious" and "severe," which are not synonymous, the following note of clarification is provided:

The term "severe" is often used to describe the severity of a specific event (as in mild, moderate, or severe myocardial infarction); the event itself, however, may be of relatively minor medical significance (such as severe headache). This is not the same as "serious," which is based on patient/event outcome or action criteria usually associated with events that pose a threat to a patient's life or functioning. Seriousness (not severity) serves as a guide for defining regulatory reporting obligations.

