**DNDi** 

RD 777/34920

DNDi- 0690- 02

In conclusion, preclinical toxicology results indicate that the main target for toxicity of DNDI-0690 is the kidney. Potential renal toxicity can be closely monitored in clinical trials through standard laboratory examinations and specific renal parameters (creatinine, BUN, Cys C).

Due to heart changes as a consequence of nephrotoxicity were considered agonal in their nature and contributory to death together with renal changes, circulating levels of troponin I will continue to be monitored in the multiple ascending dose (MAD) study in healthy subjects at admission, at last day of treatment and in case of any ECG clinically significant abnormality during the course of treatment.

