### 10.2.2.2 Dose Stopping Criteria Within a Cohort (Part A, Part B and Part C)

Dosing of subjects in the ongoing cohort will be temporarily stopped pending evaluation of all available data if any of the following criteria are fulfilled:

• A serious adverse reaction (*i.e.* a SAE considered at least possibly related to the IMP administration) occurs in one subject.

Or

• Severe non-serious adverse reactions (*i.e.* severe non-serious AE considered at least possibly related to the IMP administration) occur in two subjects in the same cohort, independent of within or not within the same system organ class.

Or

- If two or more subjects in the dose group experience any of the following:
  - ALT or AST >3xULN, considered clinically significant and IMP related.
  - Serum Cys C increase > 25%, confirmed after repeat assessment 24-48h apart, and considered IMP related
  - o Ratio of microalbuminuria/creatininuria > 300 mg/g and considered IMP related
  - o an increase in QTcF value of >60 msec from baseline (average of baseline triplicate values) or an absolute QTcF >500 msec, both confirmed by repeat measurement after 20 minutes in resting position, and considered IMP related.

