# 10.9.2 Study Variables/Endpoints

#### 10.9.2.1 Primary Endpoints

Safety parameters (changes in vital signs, ECG, safety laboratory parameters with special focus on renal function parameters, *i.e.* serum creatinine, blood urea nitrogen (BUN), and Cys C), and frequency and severity of observed TEAEs.

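### The only adverse-event severity scale has no anchor for laboratory or ECG abnormalities, so symptom-free ones default towards mild and their standing under the severe-reaction stopping criterion is unclear

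*Protocol*

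**What the plan says.** Section 10.7.4.2.2 requires every AE to be graded and gives one scale. Its lowest grade reads "Mild: An AE that is easily tolerated by the subject, causes minimal discomfort, and does not interfere with everyday activities". One step up, the moderate grade asks for enough discomfort to get in the way of daily life, with a remark that treatment might be called for. The third grade reads "Severe: An AE that prevents normal everyday activities; treatment or other intervention usually needed". Above these come a grade that turns on risk to life and a fifth for death.

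No grade cites a laboratory value, an ECG interval or a toxicity table.

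Section 10.7.4.1 makes clinically significant laboratory and procedure abnormalities AEs. For these, treatment-emergence is defined by worsening: "it is an increase in severity (clinical intensity) of the abnormality which is judged clinically significant by the Investigator".

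Severity is then used in three places:

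- **Primary endpoint (10.9.2.1):** it includes "frequency and severity of observed TEAEs".
- **AE tables (10.9.2.5.3):** subjects are tabulated by maximum severity.
- **Stopping criteria (10.2.2.2 and 10.2.2.3):** one criterion is met when severe, related, non-serious reactions "occur in two subjects in the same cohort, independent of within or not within the same system organ class".

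Section 8.5.1 names the kidney as the main target organ and adds: "Potential renal toxicity can be closely monitored in clinical trials through standard laboratory examinations".

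**The concern.** The toxicity that this protocol expects would show first in laboratory results, and possibly in nothing the subject feels. The scale measures what the subject feels and can do. Section 10.7.4.1 speaks of the intensity of the abnormality itself, which the scale has no means of expressing.

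Two things are at stake. The severity tables may show sizeable laboratory AEs as mild. And two investigators with the same symptom-free result may disagree on whether it counts towards the severe-reaction criterion. That matters because Section 10.2.2.3 ends by halting the trial, until a substantial amendment is approved, if a stopping criterion occurs in a subject on active drug. Investigators assign the grade during the trial, so an analysis plan could add tables of laboratory values but could not change the recorded AE grade.

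**Working it through.** The protocol states no figure to reproduce: the point concerns a definition, and Section 10.9.3 says the sample size has no formal basis. The check sets the passages side by side and then gives illustrations of size.

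**1. How each kind of laboratory AE meets the scale.** Section 10.7.4.1 gives three routes to clinical significance.

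| Route to being an AE | What the scale offers |
|---|---|
| Suggests disease or organ toxicity, new or evolved since screening | With no symptoms and no treatment, every term of mild is met |
| Needs medical intervention or concomitant therapy | The intervention clauses of moderate and severe may apply, but they follow a semicolon and are not stated as alternatives to the activity criterion |
| Accompanied by signs or symptoms | The activity-based scale can be used as intended |

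The first route is where the default towards mild arises. On the second route the grade is ambiguous.

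**2. How large a symptom-free finding could be.** In the CKD-EPI equation of Section 10.7.4.4.1, eGFR is proportional to (Cr/κ)^-1.209 once creatinine is at or above κ; the age, sex and race terms cancel. A doubling of creatinine from κ gives 2^-1.209 = 0.433, a fall in eGFR of about 57%. No creatinine or BUN threshold exists in Sections 10.2.2.2 or 10.2.2.3.

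**3. What the cystatin C stop catches.** Reading the protocol's equation as 130 × CysC^-1.069 × age^-0.117 − 7, take CysC 0.8 mg/L and age 35 (assumed). GFRcc falls from 101.9 to 78.8 when CysC rises by 25%, a change of −22.7%. Over an assumed 0.7 to 1.0 mg/L and ages 18 to 55, the fall is 22% to 23%. This stop does not depend on the AE grade.

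**4. How much the unclear word could matter.** Suppose each of the 6 active subjects in a cohort has independent probability p of a sizeable, related, symptom-free laboratory AE that no other criterion catches. If such events can be severe, the two-subject criterion is met with probability 1 − (1−p)^6 − 6p(1−p)^5. If they are mild, it is never met. The difference between the two readings is:

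| Assumed p | P(at least 2 of 6) |
|---|---|
| 5% | 0.033 |
| 10% | 0.114 |
| 20% | 0.345 |
| 30% | 0.580 |
| 50% | 0.891 |

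The protocol gives no p. These are upper limits on the effect, because other routes to a pause exist.

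**5. The signal already seen.** Section 8.6.1 reports an apparent 12–14% fall in creatinine-based GFR in the single-dose study. Under the CKD-EPI form, with the exponent for men, that is a creatinine rise of about 11–13% at or above κ, or 36–44% if creatinine stays below κ. The creatinine rise was judged not clinically significant, so a similar one need not become an AE or reach the scale.

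**The case against.** Three stronger readings are tempting, and the protocol supports none of them.

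- **That a symptom-free finding is mild at any size.** The intervention clauses allow a higher grade at least arguably, and the life-threatening grade turns on risk to life. The accurate statement is that the grade is undefined and leans towards mild.
- **That the scale hides the expected renal signal.** Cystatin C and the albumin/creatinine ratio stop dosing by magnitude, at the same two-subject count as the severe criterion. Creatinine, BUN and cystatin C are primary-endpoint parameters in their own right, tabulated as values and changes, and Part C measures GFR directly. Section 10.3.1 explains why creatinine may rise without renal injury and why cystatin C is preferred. QTcF above 500 msec has its own stop and its own summary category.
- **That analytes without a numeric threshold have no working stop.** The panel lists 43 blood analytes (25 biochemistry without FSH, 14 haematology, 4 coagulation), of which three (ALT, AST, serum cystatin C) have a numeric criterion. The remaining 40 are still covered in other ways. Section 10.2.2.1 discontinues the study for unacceptable safety findings of any kind, Section 10.2.1 makes escalation depend on all safety data, and one serious reaction is enough, including an important medical event. The flow-chart footnotes also re-check eligibility before each dose, although Section 10.7.2.8 mentions only Day -2.

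It can also be said that Section 10.7.4.1 leaves worsening to the investigator's judgement and does not tie it to the five grades. That is fair: a worsening can be registered. But the protocol then uses the word severity for two different things and gives a scale for only one.

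What survives is the missing anchor, its effect on the severity tables, and the unclear meaning of severe in the stopping criteria.

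**Conclusion.** The point holds in limited form. Following the text understates symptom-free laboratory and ECG AEs in the severity part of the primary endpoint. It also gives no basis for deciding whether they count as severe in Sections 10.2.2.2 and 10.2.2.3. The gap matters most for creatinine and BUN, which the primary endpoint names and which have no numeric criterion. It also touches troponin I, whose criterion is a matter of investigator judgement and applies to escalation only. For analytes with their own stop, only the severity table is affected.

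The size of the effect cannot be fixed from the protocol. The probabilities above rest on an assumed event rate, independence between subjects and no other route acting. The conclusion assumes that investigators apply Section 10.7.4.2.2 as written and that no separate grading guide says otherwise; the safety review committee charter and the safety management plan are not at hand.

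**What to change.** 1. In Section 10.7.4.2.2, limit the activity-based scale to symptomatic events.
2. Grade AEs that are laboratory or ECG abnormalities by magnitude, on a published toxicity scale named before dosing. Where an event is both symptomatic and a laboratory or ECG abnormality, record the higher grade. The choice of scale and cut-offs belongs to the sponsor and investigator.
3. Use that grade for treatment-emergent worsening in Section 10.7.4.1 and for the severity tables in Section 10.9.2.5.3.
4. Reconcile the scale with the word severe in Sections 10.2.2.2 and 10.2.2.3. Whether and how a laboratory grade counts there is for the sponsor and investigator to decide, since it could add triggers for the trial halt.

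Items 1 to 3 cost protocol and eCRF-guidance wording and no new procedures. Their downside is that some laboratory AEs will carry a higher grade than now. Item 4 touches a stopping criterion and may itself need a substantial amendment under Section 11.2.
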